## **Background and rationale**

Gastro-intestinal discomforts associated with the consumption of milk and dairy products are frequent in the general population, even in absence of lactose intolerance and casein allergy. Evidence from the literature suggests that these disorders (in the absence of other diagnoses) may be due to some peptides produced during the digestion of milk proteins. Moreover, some scientific evidence suggests that other factors, such as an altered intestinal permeability and/or a specific composition of the intestinal microbiota, may be responsible for gastrointestinal (GI) disorders resulting from milk consumption. It is also possible to hypothesize a role of the endocannabinoid system in the evolution of GI symptoms after milk ingestion given its implications in homeostatic and non-homeostatic regulation of feeding behavior, as well as in pain regulation processes.

## **Objectives**

This study aims to compare two groups of healthy (non-lactose intolerant) subjects who are irregular milk consumers, due to milk induced gastrointestinal disorders, with another group of healthy subjects who consume milk regularly, without symptoms, in relation to the primary and secondary objectives here described.

By performing a milk test in which volunteers ingest 250 ml of UHT semi-skimmed milk, primary objectives include the evaluation of:

- plasmatic response of milk-derived peptides;
- plasmatic profile of GI hormones;
- plasmatic profile of endocannabinoids and N-acyl-ethanolamines.
- urinary profile of lactose over 24 h;

Secondary objectives include the assessment of:

- baseline and postprandial plasma profile of aminoacids;
- baseline and postprandial blood glucose;
- baseline and postprandial GI symptoms;
- baseline serum concentration of dipeptidyl peptidase IV (DPPIV);
- baseline and postprandial serum activity of dipeptidyl peptidase IV (DPPIV);
- urinary excretion of indican as marker of protein digestibility;
- correlations of GI symptoms with appetite ratings and blood glucose, plasma GI hormones, plasma peptides and amino acids as well as with urinary excretion of lactose and galactose + glucose;
- the composition of the intestinal microbiota (metagenomic analysis);
- the psychological profile through questionnaires on the perception of quality of life, on levels of depression, anxiety and stress and on eating behavior.

Further secondary objectives include the assessment of:

- the prevalence of lactose malabsorption in the two groups, by using results from Lactose H2 breath test performed during the recruitment procedure;
- urinary excretion of lactulose, mannitol and sucralose as markers of intestinal permeability after an oral challenge of these 3 sugar probes.

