## Trial design

### Recruitment

The recruitment process is based on:

- **Pre-recruitment questionnaires** to collect information on dietary habits and milk-related symptoms;
- **Lactose breath test** for the assessment of final eligibility. After lactose ingestion, H2 measurements in breath will be performed over 4 hours; a cut-off value of 20 ppm over the baseline will be used to identify lactose malabsorbers. In parallel, and up to 24 hours, subjects will also record GI symptoms, through Visual Analogue Scales (VAS).

The eligibility of volunteers to participate in the study is defined on the basis of the following inclusion and exclusion criteria:

Inclusion Criteria:

- Drinking milk (maximum 150 ml/week for non-habitual milk consumers and minimum of 700 ml/week for habitual milk consumers).
- BMI between 18.5 - 30 kg/m^2.
- Availability to participate into three visits (with one week in between).
- Willing to drink 250 ml of milk in fasting condition within 10 min on one occasion.
- Signature of a written informed consent.
- Negative lactose breath test result (increase in H2 concentrations < 20 ppm vs basal value) and without symptoms or with any symptoms except "vomiting" and "Loose, mushy or watery stools".
- Lactose malabsorbers (increase in H2 concentrations > 20 ppm vs basal value but without symptoms).

Exclusion Criteria:

- Presence of any relevant organic, systemic or metabolic disease or abnormal laboratory values.
- Ascertained intestinal organic diseases, including celiac disease or inflammatory bowel diseases.
- Previous major abdominal surgeries.
- Active malignancy of any type, or history of a malignancy (patients with a history of other malignancies that have been surgically removed and who have no evidence of recurrence for at least five years before study enrolment are also acceptable).
- Untreated food intolerance.
- Lactose intolerant
- Assumption of probiotics or topical and/or systemic antibiotic therapy during the last month.
- Systematic/frequent assumption of contact laxatives.
- Pregnant and lactating women.
- Inability to conform with protocol.
- Treatment with any investigational drug within the previous 30 days.

- Recent history or suspicion of alcohol abuse or drug addiction.
- Subjects having symptoms of "vomiting" and "Loose, mushy or watery stools" at any level of severity following milk consumption and the lactose breath test

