## **Further analyses**

Since the prevalence for lactose malabsorption over the enrollment will be assessed, all the statistical analyses reported above may be applied to subgroups of subjects classified as "lactose tolerants (LT)" and "lactose malabsorbers (LM)" in order to check differences between the two groups and/or correlations between variables assessed.

Chi-means will allow to assess differences between subgroups classified on the basis of lactose absorption capacity of subjects as detected by lactose H2 breath test.

Statistical analyses and data visualization will be carried out in R environment (<http://www.r-project.org>).

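### Lactose malabsorption prevalence is to be reported in groups already filtered by the same breath test, and the plan does not define the denominator

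*Combined protocol and SAP*

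**What the plan says.** The Objectives section compares the groups on the listed primary and secondary objectives. One of the further secondary ones is "the prevalence of lactose malabsorption in the two groups, by using results from Lactose H 2 breath test performed during the recruitment procedure".

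Under Recruitment, that same test settles final eligibility: "a cut-off value of 20 ppm over the baseline will be used to identify lactose malabsorbers". The admission rules then differ by test result:

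- Test-positive volunteers are admitted as "Lactose malabsorbers (increase in H 2 concentrations > 20 ppm vs basal value but without symptoms". Any symptom removes them, and "Lactose intolerant" is also an exclusion criterion.
- Test-negative volunteers are admitted "and without symptoms or with any symptoms except 'vomiting' and 'Loose, mushy or watery stools". Only those two symptoms remove them.

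Under Allocation, the two groups of 20 are built from volunteers already found eligible. Habitual milk consumers (HMC) have no discomfort after milk. Non-habitual consumers (NHMC) drink little milk because of such discomfort. Either group may contain malabsorbers.

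The Further analyses section returns to the topic with "Since the prevalence for lactose malabsorption over the enrollment will be assessed" and does not say whether this means everyone tested or only those enrolled.

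**The concern.** A prevalence needs a denominator that was not selected on the condition being counted. Here the breath test, read together with the symptoms it provokes, removes part of the numerator before the groups exist, and it removes test-negative volunteers under a narrower rule. The malabsorber share among the 40 enrolled is then partly a product of the eligibility criteria.

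The comparison between groups is also at stake. If the rule removes a larger fraction of malabsorbers from one group than from the other, a real difference can be hidden, or a difference can appear where none exists. A reader who saw similar shares in HMC and NHMC could conclude that malabsorption is no more common in people who avoid milk, when selection could have produced the same result.

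**Working it through.** **Inputs.** The documents give no prevalence and no symptom rates, so there is no planned figure to reproduce. The structure comes from Recruitment and Allocation; every rate below is an assumption. I read the two breath-test inclusion criteria as alternatives, since no one can meet both, and assume that willingness to enrol does not depend on malabsorption.

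- p: true prevalence of malabsorption in a consumer type
- s: share of malabsorbers with any symptom (all removed)
- x: share of test-negatives with vomiting or loose stools (removed)

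**Formula.** Of all volunteers, p(1−s) are eligible malabsorbers and (1−p)(1−x) are eligible test-negatives. Hence

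enrolled prevalence = p(1−s) / [p(1−s) + (1−p)(1−x)],

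or equivalently, observed odds = true odds × (1−s)/(1−x).

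**Direction within a group.** The enrolled share is too low when s > x, correct when s = x, and too high when s < x. The symptoms that remove a malabsorber (any) include the two that remove a test-negative. So s > x fails only if having any symptom at all is no more common among malabsorbers than those two symptoms are among test-negatives.

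**Illustration.** True prevalence is 50% in NHMC and 40% in HMC, a difference of +10 points.

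HMC with s = 10%, x = 0: 0.4×0.9 / (0.4×0.9 + 0.6) = 0.36/0.96 = 37.5%.

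NHMC with x = 10%:

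| s in NHMC | Calculation | Enrolled NHMC | NHMC − HMC |
|---|---|---|---|
| 10% | 0.45/0.90 | 50% | +12.5 points |
| 40% | 0.30/0.75 | 40% | +2.5 points |
| 60% | 0.20/0.65 | 30.8% | −6.7 points |
| 80% | 0.10/0.55 | 18.2% | −19.3 points |

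The sign changes where the NHMC odds, 1×(1−s)/0.9, equal the HMC odds, 0.36/0.60 = 0.6. That gives 1−s = 0.54, so s = 46%.

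**Sensitivity to other assumptions.**

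- True 30% in HMC, s = 10% in HMC, x = 0 in both: the contrast reverses when s in NHMC exceeds 1 − 0.9/OR, where OR is the true odds ratio. The threshold is 42% if true NHMC prevalence is 40%, 61% if 50%, and 84% if 70%.
- Equal true prevalence of 40%, s = 20% in HMC and 60% in NHMC, x = 0: the enrolled shares are 34.8% and 21.1%, a spurious difference of −13.7 points.
- Equal s of 30%, x = 0, true 30% v 50%: the enrolled shares are 23.1% and 41.2%. Both are too low, but the order is kept.

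**The case against.** Five objections deserve an answer.

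1. *The denominator may already be the right one.* The Further analyses wording can be read as everyone breath-tested during enrolment, and then this selection step causes no bias. That reading is possible, so a reader should not infer that the objective cannot be answered. However, the Objectives section refers to the two groups, Allocation defines those groups as eligible subjects, and no section plans to report symptomatic malabsorbers who were screened out. The ambiguity itself needs resolving.

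2. *The study is about people who are not lactose intolerant.* This stands. Within the eligible population the enrolled share describes what it counts. It is too low only as a statement about habitual and non-habitual consumers at large, and the plan does not label it as the narrower quantity.

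3. *Heavier loss in NHMC is not documented.* This also stands. NHMC are defined by discomfort after milk, whereas the filter uses symptoms after lactose, and the Background proposes peptides, permeability and microbiota as causes. A reader might infer that the group contrast must reverse. The documents do not support that: reversal depends on assumed rates, and does not occur at s = 40% in the illustration or when s and x are equal across groups.

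4. *Harm to the rationale is conjecture.* A reader might infer that the plan sets out to show that discomfort is unrelated to lactose. The Background says only that discomfort is common even without lactose intolerance, and no such conclusion is planned.

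5. *The objective is minor and imprecise.* It is one of the further secondary objectives, with no sample size of its own. With 6 of 20, the exact 95% interval is 12% to 54%; power for 30% v 50% with 20 per group is about 25%, against 93 per group needed for 80%. This limits the importance of the point. It does not remove the bias, which a confidence interval would not show.

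**Conclusion.** The concern holds in a conditional form. If prevalence is computed in the enrolled groups, as the Objectives wording most naturally implies, it understates prevalence among consumers at large whenever s exceeds x. That condition is weak, because the removing symptoms for test-negatives are a subset of those for malabsorbers.

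Distortion of the group contrast needs a further assumption: that (1−s)/(1−x) is smaller in NHMC. The group definitions make this plausible but do not establish it. Under it, a true +10 points can shrink to +2.5 or turn into −6.7, depending on whether 40% or 60% of NHMC malabsorbers are symptomatic. These figures illustrate the mechanism and are not estimates for this trial.

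The primary endpoints are not affected by this point. It should be corrected because the correction is cheap and uses a test that is already performed.

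**What to change.** In Objectives and in Further analyses:

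- Define the prevalence denominator as all volunteers who completed the recruitment breath test, classified as habitual or non-habitual consumers from the pre-recruitment questionnaire, before any breath-test or symptom exclusion.
- Report the number excluded for symptoms, by breath-test result and consumer type.
- State which questionnaire exclusions were applied before the test. Vomiting or loose stools after milk is itself an exclusion criterion, so if it is applied first, the breath-tested set is less selected than the enrolled groups but not unselected. That limit should be reported with the estimate.
- Label the figure in the 20 + 20 enrolled subjects as the malabsorber share among eligible subjects only.

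No new procedure and no change to eligibility is needed. The cost is SAP wording and retention of screening data for volunteers who are not enrolled. The one downside is that the consent form must cover use of those data.

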## Trial design

### Recruitment

The recruitment process is based on:

- **Pre-recruitment questionnaires** to collect information on dietary habits and milk-related symptoms;
- **Lactose breath test** for the assessment of final eligibility. After lactose ingestion, H2 measurements in breath will be performed over 4 hours; a cut-off value of 20 ppm over the baseline will be used to identify lactose malabsorbers. In parallel, and up to 24 hours, subjects will also record GI symptoms, through Visual Analogue Scales (VAS).

The eligibility of volunteers to participate in the study is defined on the basis of the following inclusion and exclusion criteria:

Inclusion Criteria:

- Drinking milk (maximum 150 ml/week for non-habitual milk consumers and minimum of 700 ml/week for habitual milk consumers).
- BMI between 18.5 - 30 kg/m^2.
- Availability to participate into three visits (with one week in between).
- Willing to drink 250 ml of milk in fasting condition within 10 min on one occasion.
- Signature of a written informed consent.
- Negative lactose breath test result (increase in H2 concentrations < 20 ppm vs basal value) and without symptoms or with any symptoms except "vomiting" and "Loose, mushy or watery stools".
- Lactose malabsorbers (increase in H2 concentrations > 20 ppm vs basal value but without symptoms).

Exclusion Criteria:

- Presence of any relevant organic, systemic or metabolic disease or abnormal laboratory values.
- Ascertained intestinal organic diseases, including celiac disease or inflammatory bowel diseases.
- Previous major abdominal surgeries.
- Active malignancy of any type, or history of a malignancy (patients with a history of other malignancies that have been surgically removed and who have no evidence of recurrence for at least five years before study enrolment are also acceptable).
- Untreated food intolerance.
- Lactose intolerant
- Assumption of probiotics or topical and/or systemic antibiotic therapy during the last month.
- Systematic/frequent assumption of contact laxatives.
- Pregnant and lactating women.
- Inability to conform with protocol.
- Treatment with any investigational drug within the previous 30 days.

- Recent history or suspicion of alcohol abuse or drug addiction.
- Subjects having symptoms of "vomiting" and "Loose, mushy or watery stools" at any level of severity following milk consumption and the lactose breath test

## Allocation

Subjects who will be assessed as eligible and will accept to enter the study protocol, will be allocated in the proper group, and the enrollment will be concluded when 2 groups of subjects will be constituted as follows:

- **Group 1**, habitual milk consumers (HMC): 20 subjects who are regular milk consumers ( $>700$  mL/week), do not experience GI discomforts after milk intake and are lactose tolerant or lactose malabsorber.
- **Group 2**, non-habitual milk consumers (NHMC): 20 subjects who are not regular milk consumers ( $< 150$  mL/week), because of GI discomforts after milk intake and are lactose tolerant or lactose malabsorber.

## Intervention and other measures/samples

The study protocol includes a gut permeability test and a milk test to be performed for all subjects from both groups after one week from the lactose breath test and with one week in between.

### *Gut permeability test*

Subjects will receive instruction to avoid medicine consumption and to follow a controlled diet for 2 days before the test (avoiding milk and dairy products, and food products containing polyols that were included in a list of products they received).

Fasting subjects will collect a baseline urine sample, before drinking a solution containing 5 g lactulose, 2 g mannitol and 2 g sucralose in 100 ml of water. Urines will be collected for time periods 0-5 hours and 5-24 hours in two containers containing 1 mL of a chlorhexidine solution at 1 ppm.

Urine samples collected over 24 hours and delivered the day after to the study centre will be aliquoted (1.5 ml) and frozen at  $-40^{\circ}\text{C}$  until analyses that include lactulose, mannitol and sucralose concentration and baseline creatinine concentration.

The ratio between lactulose and mannitol (L / M) in the urine collected within the first 5 hours will represent permeability in the small intestine, while the total amount of sucralose excreted in urine in the 24 hours will be used to evaluate the colonic permeability.

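### The diet rules for the permeability test neither name sucralose nor cover the 24-hour urine collection, so dietary sucralose can add to the colonic permeability index

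*Combined protocol and SAP*

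**What the plan says.** The Gut permeability test section tells subjects "to follow a controlled diet for 2 days before the test". It describes that diet in one parenthesis: "avoiding milk and dairy products, and food products containing polyols that were included in a list of products they received". The list itself is not reproduced.

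Subjects give a baseline urine and then drink "a solution containing 5 g lactulose, 2 g mannitol and 2 g sucralose in 100 ml of water". On collection the section states: "Urines will be collected for time periods 0-5 hours and 5-24 hours". The assays are "analyses that include lactulose, mannitol and sucralose concentration and baseline creatinine concentration". It is not said whether the three probes are measured in the baseline sample, and no baseline subtraction is described.

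Two indices follow. Small-intestinal permeability is the lactulose/mannitol ratio in the first 5 hours. For the colon, "the total amount of sucralose excreted in urine in the 24 hours will be used to evaluate the colonic permeability". The Objectives section places these measures among the further secondary objectives: "urinary excretion of lactulose, mannitol and sucralose as markers of intestinal permeability after an oral challenge of these 3 sugar probes".

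**The concern.** The challenge uses three probes. The polyol restriction controls dietary mannitol. It does not reach sucralose, a chlorinated disaccharide sweetener found in some drinks, table sweeteners and sugar-free foods. As written, a subject can follow the instruction fully and still take in sucralose, both before the test drink and while urine is being collected.

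The gap falls on the more exposed of the two indices. It uses a single probe, it is an absolute amount with no denominator, and it runs over 24 hours in which subjects will eat. The fasting urine comes before the drink and carries no information on later intake.

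At stake is the reading of one between-group comparison. Altered intestinal permeability is among the mechanisms named in the Background and rationale. Under Allocation, the groups are formed by milk habit and milk-related discomfort rather than by randomisation, so nothing in the design balances sweetener use between them. A difference in that habit would be read as a difference in colonic permeability.

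**Working it through.** **What the text controls.** The Gut permeability test and Milk test sections can be set side by side.

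- Before the test: the permeability test has a 2-day restriction on dairy and on listed foods containing polyols; the milk test has a 2-day restriction on milk, dairy and foods with milk protein.
- During the 24 hours: the permeability test states no restriction, meal or diary; the milk test has a lunch at the centre, a fixed dinner and a 1-day food diary.

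The milk test also has a food diary in the week before it. Depending on the order of the tests and the diary's first day, this might touch the permeability collection, but the text does not link the two. The food frequency questionnaire is semi-quantitative and describes habitual intake, not intake on the test day.

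**No plan figure to reproduce.** The Sample size calculation section covers BCM-7, urinary lactose, breath hydrogen, and GI hormones with endocannabinoids. It gives no variance, recovery or target difference for sucralose.

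**Size for one subject.** Inputs: probe 2 g = 2000 mg (documents); dietary sucralose S mg (assumed); the same fractional recovery r for dietary and probe sucralose (assumed).

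Measured amount = r × (2000 + S). Relative rise over the probe alone = S / 2000, because r cancels.

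- S = 50 mg: 50/2000 = 2.5%
- S = 200 mg: 200/2000 = 10%
- S = 400 mg: 400/2000 = 20%

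Sucralose eaten late in the window would be only partly recovered by 24 hours, so its contribution would be smaller.

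**Effect on the group comparison.** Inputs: 20 per group and two-sided 5% (documents); difference D in group mean intake and between-subject CV (both assumed). With no true difference in permeability, the bias as a fraction of the probe mean is b = D/2000 and the standard error is se = CV × √(2/20). By the normal approximation, the false-positive rate is Φ(b/se − 1.96) + Φ(−b/se − 1.96).

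Example: D = 200 mg and CV = 30% give b = 0.10, se = 0.30 × 0.316 = 0.095 and b/se = 1.05, hence 18.4%.

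| Difference in mean intake | CV 30% | CV 50% | CV 70% |
|---|---|---|---|
| 50 mg | 5.8% | 5.3% | 5.2% |
| 100 mg | 8.2% | 6.2% | 5.6% |
| 200 mg | 18.4% | 9.7% | 7.4% |

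If mean intake is equal in the two groups, D = 0 and the rate stays at 5%.

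**Noise.** If dietary intake has an SD of 100 mg (assumed; 100/2000 = 5% of the probe), a CV of 30% becomes √(0.30² + 0.05²) = 30.4%, and a CV of 50% becomes √(0.50² + 0.05²) = 50.2%. The loss of precision is negligible.

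**The case against.** The strongest objection is that the deciding document is not available. Subjects receive a product list that the protocol only summarises, and it may already include sucralose-sweetened products. This stands in part. A reader might infer that such products are permitted; the documents support only that the text does not exclude them. The objection does not cover the collection period, for which no restriction of any kind is stated.

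A second objection concerns size. The probe is large, 400 mg is assumed as a heavy user's intake, and a single subject's intake is not a between-group bias. Nothing in the documents suggests that sweetener use differs by milk habit. This also stands: a 50 mg difference in group means hardly moves the error rate, and the added noise is trivial. What remains is that the groups are not randomised and the plan has no means of showing that intake is equal.

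A reader might also reach for larger figures by attributing all dietary sucralose to the 5–24 hour urine. If half of the probe excretion fell there, the same three intakes would raise that fraction by 5%, 20% and 40%. The plan does not use that fraction as its index. The colonic measure is the 24-hour total, so these figures do not apply.

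Finally, the baseline urine might seem to solve the problem. It could show carry-over from before the test if sucralose were assayed in it, which the text does not clearly say. It cannot show intake during the collection.

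**Conclusion.** The concern holds in a limited form. As described, the diet restriction does not name one of the three probes and is not stated to continue through the collection, while the colonic index is an uncorrected absolute amount of that probe. Dietary sucralose can therefore add to it, by 2.5% to 20% for assumed intakes of 50 to 400 mg with equal fractional recovery.

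It would be too strong to say that the comparison is biased. Bias needs a difference in mean intake between the groups, which the documents neither show nor rule out. On assumed CVs of 30% to 70%, a 50 mg difference moves the 5% error to between 5.2% and 5.8%, and a 200 mg difference to between 7.4% and 18.4%.

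The reach is narrow: one further secondary measure. The lactulose/mannitol ratio, the primary endpoints and the stated sample size do not depend on it. The change is worth making because it is cheap beforehand, whereas sucralose eaten during the collection cannot be told apart from the probe in the urine.

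**What to change.** Add sucralose (E955) and products sweetened with it to the list of products to avoid. State in the Gut permeability test section that this item applies for the 2 days before the test and until the last urine of the 24-hour collection. If the list already covers sucralose, say so and add only the extension.

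Optionally, state that sucralose is assayed in the baseline urine already collected, fix a threshold for pre-test carry-over in advance, and repeat the colonic comparison without the subjects above it. Present this as a sensitivity analysis and a partial check: it reduces groups of 20 and cannot detect intake during the collection.

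The main change costs one more list item, one sentence of instruction and a slightly stricter diet for about 3 days (2 days before plus the 24-hour collection). The optional check costs up to 40 baseline assays (2 × 20), if these are not already planned, and one additional analysis. No sample size or power figure in the plan changes.
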